7.4. Additional Assessments

7.4.1. Number of Injections and Dose of rFVIII Fc to Resolve a Bleeding Episode

The number of injections, average dose per injection (IU/kg), and total dose (IU/kg) required to resolve a bleeding episode will be determined on both a per-bleeding episode and per-subject basis. See Section 7.1.1 for details on the definition of a bleeding episode. A bleeding episode is considered resolved when treatment for the bleeding is no longer needed.

Per bleeding episode: The total number of injections will include the initial injection for a spontaneous bleed (SB), a traumatic bleed (TB), or a bleed of unknown type plus all injections identified as follow-up (FU) treatment for that bleed. For each bleed, the average dose per injection will be calculated as the average of all doses (IU/kg) administered among the SB/TB/Unknown and FU injections administered to treat that bleed; the total dose will be the sum of these doses. The number of injections required for the resolution of a bleeding episode will be summarized across all bleeding episodes in study 8HA01EXT both categorically (1, 2, 3, >3; 1, >1; and ≤ 2 , >2) and with descriptive statistics. The average dose per injection and total dose required for resolution of a bleeding episode will be summarized using descriptive statistics.

Per subject: The number of injections, average dose per injection, and total dose required to resolve each bleeding episode, as determined for the per-bleeding episode summaries, will be averaged across all bleeding episodes in study 8HA01EXT for each subject. The average number of injections required for resolution of a bleeding episode will be summarized both categorically (1 to <2, 2 to <3, and ≥ 3) and with descriptive statistics. The averages for the per-subject average dose per injection and total dose required for resolution of a bleeding episode will be summarized using descriptive statistics.

Bleeding episodes that were treated with both study and non-study medication will be included in the determination of the number of injections required to resolve the bleeding episode but not in either the average dose per injection or total dose required.

For the above analysis, data from the FAS will be summarized.

7.4.2. Time from Last Injection of rFVIII Fc to a Bleeding Episode

The time (in days) between a spontaneous bleeding episode and the most recent previous prophylaxis injection of rFVIII Fc, will be calculated and summarized using descriptive statistics. Time will be determined in minutes and then converted to days as total minutes divided by 1440. Of note, the reference time for the bleeding episode is the onset of the bleed and not the time treatment for the bleed was first administered. The definition of a new bleeding episode can be found in Section 7.1.1.

The time from the last prophylactic injection to a new spontaneous bleeding episode will be determined on both a per-bleeding episode and per-subject basis. Each evaluable spontaneous bleeding episode will be included as a separate observation in the summary statistics for the per-bleeding episode evaluation. Evaluable bleeding episodes are those for which both a date and time are available for both the onset of the bleeding episode and the previous prophylactic injection. For the per-subject evaluations, times will be averaged across all evaluable spontaneous bleeding episodes per subject and descriptive statistics will be provided for this per-subject average time.

Bleeding episodes that were treated with non-study medication will be included in these analyses, regardless of which treatment was administered first, if all other information needed to calculate the endpoint value is available.

7.4.3. Time Between the First and Second Injection to Treat a Bleeding Episode

In order to characterize the resolution of bleeding episodes treated with rFVIII-Fc, the time between the first and second injections to treat a bleeding episode will be determined on both a per-bleeding episode and a per-subject basis.

Per bleeding episode: The time (in hours) between the first and second injections to treat a bleed will be summarized using descriptive statistics across all bleeding episodes, including those with type=Unknown, that required at least 2 injections for resolution.

Per subject: The number of hours between the first and second injections to treat a bleeding episode, as determined for the per-bleeding episode summaries, will be averaged across all evaluable bleeding episodes per subject. Descriptive statistics will be provided for the per-subject average times.

Additionally, the time between the first and second injections to treat a bleed will be summarized per bleeding episode and per subject by type of bleed (spontaneous, traumatic) using descriptive statistics.

Bleeding episodes that were treated with non-study medication will be included in the determination of the time between the first and second injections.

7.4.4. Hemophilia Joint Health Score

Joint assessment will be collected using a modified Hemophilia Joint Health Score (HJHS) for adult subjects and use the HJHS for pediatric subjects.

The Modified HJHS assessment includes the scoring of six joints (left ankle, right ankle, left elbow, right elbow, left knee, right knee) on a scale from 0 to 19 according to the following criteria: swelling, duration, muscle atrophy, crepitus, flexion loss, extension loss, instability, joint pain, and strength. Gait will be scored on a scale from 0 to 2 based on walking and climbing stairs. The total score will be the sum of scores from all 6 joints plus the gait score (range from 0 to 116, with 0 being normal and 116 being the most severe disease).

The HJHS assessment includes the scoring of six joints (left ankle, right ankle, left elbow, right elbow, left knee, and right knee) on a scale from 0 to 20 according to the following criteria: swelling, duration of swelling, muscle atrophy, crepitus of motion, flexion loss, extension loss, joint pain, and strength. Gait will be scored on a scale from 0 to 4 based on the number of skills that are not within the normal limits. The total score will be the sum of scores from all six joints plus the gait score (range from 0 to 124, with 0 being normal and 124 being the most severe disease).

The total and gait scores and change from study 8HA01EXT baseline will be summarized by visit for overall treatment regimen for Safety Analysis Set. The study 8HA01EXT baseline is defined above in Section 5.1.

Modified HJHS and HJHS scoring details are given in [Appendix H](#).

7.5. Endpoints Based on Patient-reported Outcomes

The following patient-reported outcomes will be assessed and data listings will be provided. Analyses involving baseline value will be based on study 8HA01EXT Baseline (as defined above in Section 5.1).

7.5.1. HAEMO-QoL and HAEM-A-QoL

The questionnaires will be analyzed according to the recommendations of the questionnaire authors (see <http://www.haemoqol.de>). Details of the questionnaire are provided in Appendix C.

The algorithm for deriving the sub scores is given in Appendix C.

The HAEMO-QoL questionnaire for Children and Teenagers aged 13-16 contains 12 sub-grouped sections, which will count as 12 separate sub-scores. Further details on the sub-scores are contained in Appendix C. The following sub-sections make up the 12 sub-scores of the HAEMO-QoL questionnaire:

Time Period	Sub-scores for HAEMO-QoL
During the past month	1. Physical health 2. Feeling 3. View of yourself 4. Family 5. Friends 6. Perceived support 7. Others persons 8. Sports and school 9. Dealing with hemophilia 10. Treatment 11. Future 12. Relationships

The HAEM-A-QoL questionnaire for Adults contains 10 sub-grouped sections, which will count as 10 separate sub-scores. The following sub-sections make up the 10 sub-scores of the HAEM-A-QoL questionnaire:

Time Period	Sub-scores for HAEM-A-QoL
During the past month	1. Physical health 2. Feeling of yourself 3. View 4. Sports and leisure 5. Work and school 6. Dealing with hemophilia 7. Treatment
Recently	8. Future 9. Family planning 10. Partnership and sexuality

As specified in Appendix C, questions will either have been coded or will be re-coded to ensure that high scores represent a low quality of life and low scores represent a high quality of life. These scores are then transformed to produce a Transformed Scale Score (TSS). This score is

scaled, as a percentage, from 0 to 100%, with higher TSS values representing a worst quality of life for each sub-score and total score summary measurement.

For both the HAEMO-QoL and HAEM-A-QoL questionnaires the total scores and individual sub-scores based on the TSS will be summarized for the observed value and change from study 8HA01EXT baseline for the FAS.

7.5.2. Hemo-Sat Patient Satisfaction Scale

A copy of the questionnaire and further details on the subscales and the calculation of the subscores are contained in Appendix F.

As specified in Appendix F, questions will either have been coded or will need to be re-coded to ensure that high scores represent a low satisfaction and low scores represent a high satisfaction. These scores are then transformed to produce a Transformed Scale Score (TSS). This score is scaled as a percentage from 0 to 100% for each sub-score and total score, with higher TSS values representing a worst satisfaction.

The total score and individual subscores based on the TSS will be summarized for the observed response and change from baseline using descriptive statistics for the FAS. A negative change from baseline represents an improvement in satisfaction. Summaries will be at each visit. See Section 5.1.3 for details of when questionnaire results should be excluded from tabulated summaries.

7.5.3. CHO-KLAT

Two forms of the assessment tool were administered for subjects from 8HA02PED, one to the subjects (Child Self-report Questionnaire), and one to the parent/caregiver (Parent/Proxy Questionnaire).

A copy of the questionnaires and details on their scoring are provided in Appendix E. As specified in Appendix E, questions will either have been coded or will need to be re-coded to ensure that high scores represent a high quality of life and low scores represent a low quality of life. These scores are then transformed to produce a Transformed Scale Score (TSS). This score is scaled, as a percentage, from 0 to 100%, with higher TSS values representing a better quality of life.

The total score based on the TSS will be summarized for the observed response and change from study 8HA01EXT baseline using descriptive statistics for subjects ≥ 5 years old in study 8HA02PED. A positive change from baseline represents an improvement in quality of life. Summaries will be at each visit. See Section 5.1.3 and Appendix E for details of when questionnaire results should be excluded from tabulated summaries.

7.5.4. EQ-5D Youth Questionnaire

The EQ-5D™ is a standardized instrument used to measure health outcome. EQ-5D-Y is a version of this instrument developed for use in children aged 7 to 12 years old.

The questionnaire will be analyzed according to the recommendations of the authors (see www.euroqol.org). EQ-5D-Y consists of 2 pages – a 5 dimension descriptive system and the EQ visual analogue scale. The elements of the questionnaire are provided in Appendix G.

The descriptive system contains 5 categories: mobility; looking after myself; doing usual activities; having pain or discomfort; and feeling worried, sad, or unhappy. Each category has 3 levels of response representing no problems, some problems, and a lot of problems.

The EQ visual analogue scale is a visual scale from 0 to 100 used to record a subject's overall self-rated health state. The subject is asked to mark an 'X' on the scale then record the corresponding number; 0 refers to the worst possible health state, 100 refers to the best possible health state.

The EQ visual analogue scale will be summarized for the observed response and change from study 8HA01EXT baseline using descriptive statistics for children 7 to <12 years of age for the FAS. Subjects for whom the baseline value is zero will be excluded from this analysis. See Section 5.1.3 for details of when questionnaire results should be excluded from tabulated summaries.

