16.5.2. Methods of Analysis

16.5.2.1. Patient-Reported Outcomes

Questionnaires for patient-reported outcomes are described in Section [13.5.2](#).

Endpoints for patient-reported outcomes (Haem-A-QoL, Haemo-QoL, Hemo-Sat-P, CHO-KLAT Children, CHO-KLAT Proxy, EQ-5D-Y and EQ-5D-3L) will be analyzed in a separate report. These endpoints will be analyzed by summarizing actual values, change from baseline and percent change from baseline, as appropriate.

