5.1.3. Handling of Missing Data

Aside from the following, no imputation of study data will be performed.

- The episodic treatment regimen at the start of study 8HA01EXT will be imputed for the scenario specified in Section 5.3.1.
- The end of PK period of the parent study (997HA307 or 997HA309) and start of study 8HA01EXT will be imputed for the scenario specified in Section 5.3.1.
- The occurrence of a new bleeding episode will be imputed if >72 hours lapse between 2 consecutive injections administered to treat a bleed. Details are provided in Section 7.1.1.

For CHO-KLAT, if a subject has data missing at a particular visit, the total score can still be estimated provided at least 27 of the 35 questions have been answered. If a subject's data cannot be used to calculate an overall score that subject will also be excluded from summaries of individual domains at that visit and will be flagged as excluded from summaries in analysis dataset. Details are provided in Section 7.5.3 and Appendix E.

For HAEMO-QoL and HAEM-A-QoL, Hemo-Sat, EQ-5D-Y and EQ-5D-3L, if a subject has data missing at a particular visit for a domain, the total score and subscores will still be estimated provided the questionnaire makes provision for missing domains in the calculation algorithm of overall score. If a subject's data cannot be used to calculate an overall score that subject will also be excluded from summaries of individual domains at that visit and will be flagged as excluded from summaries in data listings. Details are provided in Sections 7.5.1, 7.5.2, 7.5.4 and 7.5.5 Appendix C, F, G, and D, respectively.

For the analysis of AEs and concomitant medications/procedures, if the stop/start date of an AE/concomitant medication is missing or partial, the corresponding study day will be left blank. However, inferences will be made from the partial and missing dates to classify medications as concomitant, AEs as treatment emergent (or not) and AEs during surgical/rehabilitation period. These inferences are described in Sections 6.4.1 and 8.2, respectively.

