7.5.5. EQ-5D-3L Questionnaire

The questionnaire will be analyzed according to the recommendations of the authors (see www.euroqol.org). EQ-5D consists of 2 pages – a 5 dimension descriptive system and the EQ visual analogue scale. A copy of the questionnaire is provided in Appendix D.

The descriptive system contains 5 categories: mobility, self-care, usual activities, pain/discomfort and anxiety/depression. These categories are scored on a scale of 1 to 3, with 1 being the best response, and 3 being the worst response. A total score can also be calculated for the EQ-5D-3L questionnaire. For ease of interpretation, these scores will be transformed into a 0-100 scale by using the following steps:

- Sum all of the sub-category scores (can take values from 5-15) and divide by the maximum possible score overall (3 x 5 categories = 15). If all questions within each sub-category are missed, exclude these from analysis.
- The total score is calculated as: $100 * (\text{subject total score} / \text{maximum possible score})$

The 5 categories and total will be summarized for the observed response and change from the study 8HA01EXT baseline for the FAS. See Section 5.1.3 for details of when questionnaire results should be excluded from tabulated summaries.

The EQ visual analogue scale is a visual scale from 0-100 to record a respondent's overall self-rated health state. The respondent is asked to mark an 'X' on the scale then record the corresponding number; 0 refers to the worst possible health state, 100 refers to the best possible health state. This will also be presented alongside the 5 dimension descriptive system scores. The EQ visual analogue scale will be summarized for the observed response and change from the study 8HA01EXT baseline for the FAS. See Section 5.1.3 for details of when questionnaire results should be excluded from tabulated summaries.

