Subjects from study 8HA02PED: Summary of annualized bleeding rate by location and type of bleeds

Subjects from study 8HA02PED: Summary of annualized bleeding rate by the presence of target joints at screening in parent study

Subjects from study 8HA02PED: Summary of annualized bleeding rate by ePD entry compliance
Summary of subject's assessment of response to rFVIII Fc injections for the treatment of bleeding episodes

Summary of number of injections required for resolution of a bleeding episode

Summary of dose (IU/kg) of rFVIII Fc for resolution of bleeds

Summary of results and change from study 8HA01EXT baseline: CHO-KLAT total score from the Child Self-report Questionnaire

Summary of results and change from study 8HA01EXT baseline: CHO-KLAT total score from the Parent/Proxy Questionnaire

Summary of results and change from study 8HA01EXT baseline: Hemo-Sat total score and subscores

Summary of EQ-5D-Y descriptive system

Summary of results and change from study 8HA01EXT baseline: EQ-5D-Y visual analogue scale

Summary of hemophilia-related health-economic parameters

Summary of health economic parameters for all physician and emergency room visits

Summary of results and changes from study 8HA01EXT: Hemophilia Joint Health Score (HJHS)

Overall groups of subjects in 8HA01EXT (as described in Section 5.1):

Summary of compliance for the treatment of bleeding episodes

Summary of prophylactic dose compliance

Summary of prophylactic dosing interval compliance

Summary of prophylactic compliance

Summary of EPD entry compliance

Overall summary of rFVIII Fc treatment-emergent adverse events

Summary of rFVIII Fc treatment-emergent adverse events by preferred term in descending order of incidence

Summary of rFVIII Fc treatment-emergent adverse events by relationship to treatment

Summary of rFVIII Fc treatment-emergent serious adverse events

Summary of anti-rFIIIV Fc antibodies

Surgery subgroup – Summary of Investigators'/Surgeons' assessment of subjects' hemostatic response to rFVIII Fc post major surgery

Surgery subgroup – Number of injections and dose required to maintain hemostasis during major surgery

Surgery subgroup - Estimated total blood loss during major surgery

Surgery subgroup – Total rFVIII Fc consumption (IU/kg) per major surgery

Surgery subgroup - summary of number of bleeds after surgery per major surgery

Summary of Investigators'/Surgeons' assessment of subjects' hemostatic response to rFVIII Fc post minor surgery

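### SAP 7.5.4 drops children with a baseline EQ-5D-Y VAS of 0 from summaries of observed value and change, although 0 is a valid score and both statistics can be computed from it

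*SAP*

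**What the plan says.** SAP 7.5.4 describes the EQ-5D-Y VAS as a 0 to 100 self-rating and gives the meaning of its ends: "0 refers to the worst possible health state, 100 refers to the best possible health state". The planned analysis, for ages 7 to under 12 in the Full Analysis Set, reads in part: "The EQ visual analogue scale will be summarized for the observed response and change from study 8HA01EXT baseline using descriptive statistics for children 7 to" (the quote stops before the upper age limit). The next sentence is the exclusion: "Subjects for whom the baseline value is zero will be excluded from this analysis". No reason is given. The section then refers to SAP 5.1.3 for when questionnaire results are left out of tables.

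Other places bear on this point:

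- **SAP 5.1.3** deals with missing data, visit by visit: "If a subject's data cannot be used to calculate an overall score that subject will also be excluded from summaries of individual domains at that" (the quote stops one word short). It does not mention a zero baseline.
- **SAP 5.1.2** bases by-visit change summaries on subjects with both a baseline and a post-baseline value at that visit.
- **SAP list of tables** (subjects from 8HA02PED) has one VAS table: "Summary of results and change from study 8HA01EXT baseline: EQ-5D-Y visual analogue scale".
- **SAP 7.5.5** covers the EQ-5D-3L VAS, with the same range and the same meaning of 0: "The EQ visual analogue scale will be summarized for the observed response and change from the study 8HA01EXT baseline for the FAS". It has no zero-baseline rule.
- **Protocol 16.5.2.1**, which names the EQ-5D-Y among the instruments, says: "These endpoints will be analyzed by summarizing actual values, change from baseline and percent change from baseline, as appropriate". The protocol synopsis lists actual values and change, without percent change.

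**The concern.** A rule that drops subjects because their baseline is zero is normally there to avoid division by zero in a percent change. Here it is attached to two statistics that need no division by the baseline. Because it refers to the analysis described in the sentence just before it, it covers a child's observed scores at every visit as well as the change.

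The children removed are defined by their value on the outcome itself, at its worst point. Two things follow if any such child exists. The baseline mean of those left is too high as a description of the children who answered. The change summary also loses children who can stay the same or improve but cannot get worse. In a group this small, one child can move a mean by several points.

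**Working it through.** There is no stated figure to reproduce: the plan gives no sample size, expected mean or SD for this scale. The check has two parts.

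**1. Which statistics fail at a baseline of 0?** Take a child who scores 0 at baseline and 50 later.

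- Observed values: 0 and 50, both valid scores.
- Change = post − baseline = 50 − 0 = +50.
- Percent change = 100 × (post − baseline) / baseline = 100 × 50 / 0, undefined.

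Only the third fails. It appears neither in SAP 7.5.4 nor in the title of the planned VAS table. The child has a baseline and a post-baseline value, so he meets the SAP 5.1.2 condition for the change summary. Nothing is missing, so SAP 5.1.3 does not exclude him. An adult with the same two scores would be kept under SAP 7.5.5. So would a child with a transformed CHO-KLAT score of 0 at baseline, although 0 is also the worst score on that scale (SAP 7.5.3).

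**2. How far could the means move?** The inputs are assumptions, because the documents contain no VAS data. Of n children, k score 0 at baseline and v at a later visit. The others have a mean baseline of 80 and a mean change of 0. The values of n are set only to the right order of size: Protocol 5.1.3 plans 25 children aged 6 to under 12 in the pediatric parent study, and this analysis starts at age 7.

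- Baseline mean with everyone = (n − k) × 80 / n; after exclusion = 80.
- Mean change with everyone = k × v / n; after exclusion = 0.

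For n = 20 and k = 1, the baseline mean is 19 × 80 / 20 = 76 against 80. With v = 50, the mean change is 50 / 20 = 2.5 against 0. The range is:

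| n | k | Baseline mean, all | Baseline mean, zeros excluded | Mean change, all (v = 0 / 50 / 80) | Mean change, zeros excluded |
|---|---|---|---|---|---|
| any | 0 | 80.0 | 80.0 | 0 | 0 |
| 25 | 1 | 76.8 | 80.0 | 0 / 2.0 / 3.2 | 0 |
| 20 | 1 | 76.0 | 80.0 | 0 / 2.5 / 4.0 | 0 |
| 15 | 1 | 74.7 | 80.0 | 0 / 3.3 / 5.3 | 0 |
| 25 | 2 | 73.6 | 80.0 | 0 / 4.0 / 6.4 | 0 |
| 15 | 2 | 69.3 | 80.0 | 0 / 6.7 / 10.7 | 0 |

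The rise in the baseline mean is certain whenever a zero is removed and the remaining scores are not all zero. The effect on mean change is not certain. It is nil if the child stays at 0 and the others do not change. It would reverse if the other children improved on average by more than the excluded child.

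**The case against.** **Percent change.** The protocol body allows for percent change on the patient-reported scales, so the sentence may be left over from such an analysis. That origin is an inference. It would justify keeping a zero-baseline rule for percent change, if reported, but not for observed values or change. This part stands to the extent that plain deletion would leave percent change, if later added, without a rule.

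**Developers' recommendations.** SAP 7.5.4 says the questionnaire follows its developers' recommendations, which cannot be checked here. SAP 7.5.5 refers to the same source for the same scale and draws no such exclusion from it.

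**Data errors.** A zero might be suspected as an entry error. The SAP does not say so, and automatic exclusion cannot separate errors from true answers.

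**Low consequence.** This stands. All analyses are descriptive, and patient-reported outcomes are listed apart from the primary and secondary endpoints. The five EQ-5D-Y dimensions have their own table, which the rule does not touch. A baseline of exactly 0 may not occur.

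**Stronger readings.** A reader might infer that the rule removes children who are bound to improve. The documents do not support that: a child at 0 may remain at 0. A reader might also infer that it distorts a comparison of children with adults. SAP 5.1 analyses the pediatric group separately from the others, the VAS tables are separate, and no comparison is planned. The difference from SAP 7.5.5 matters only as evidence that the exclusion is not needed for this scale.

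**Conclusion.** The point holds as a minor error in a descriptive patient-reported outcome table. As written, SAP 7.5.4 discards valid observed values and computable changes from children at the bottom of the scale, and nothing in either document gives a reason. The effect is zero if no child has a baseline of 0. If one or two do, the assumptions above (others averaging 80, 15 to 25 children) put the upward shift in the baseline mean between 3.2 and 10.7 points. The shift in mean change depends on how those children and the others later score. Nothing in the documents shows that any child is affected, and neither the primary endpoint nor any secondary endpoint depends on this table. It would be wrong to conclude from this point that the trial's reported quality of life is biased.

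**What to change.** Delete the zero-baseline sentence from SAP 7.5.4. If a percent-change summary under Protocol 16.5.2.1 is to be reported, keep the sentence but confine it to that summary, and footnote how many children it leaves out.

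State the denominators explicitly. Observed values should be summarised for all children aged 7 to under 12 with a VAS value at the visit. Change should be summarised for those with both a baseline and a post-baseline value at that visit, as SAP 5.1.2 already requires. The paired-data condition belongs to the change summary only and should not be carried over to observed values.

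The cost is one sentence in the SAP and, at most, one filter removed from one table program. No new data are needed.
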